4.3 Sample Size

The primary immunogenicity objective of the study is to evaluate whether vaccination with monovalent H7N9 virus vaccine containing 1.9 µg, 3.75 µg or 7.5 µg of HA adjuvanted with AS03_A or AS03_B elicits an HI antibody response to the vaccine-homologous virus that meets or exceeds the [US FDA, CBER](#) immunogenicity criteria at the Day 43 visit.

The age-appropriate CBER criteria will be used and assessed separately:

- CBER immunogenicity criteria for SCR for 18 to 64 years of age will be shown if the lower limit (LL) of the 99.17% CI for SCR meets or exceeds 40%.
- CBER immunogenicity criteria for SPR for 18 to 64 years of age will be shown if the LL of the 99.17% CI for the incidence rate of HI Reciprocal Titers ≥ 40 meets or exceeds 70%.
- CBER immunogenicity criteria for SCR for ≥ 65 years of age will be shown if the LL of the 99.17% CI for seroconversion rate meets or exceeds 30%.
- CBER immunogenicity criteria for SPR for ≥ 65 years of age will be shown if the LL of the 99.17% CI for the incidence rate of HI Reciprocal Titers ≥ 40 meets or exceeds 60%.

The statistical testing sequence is illustrated below. The 6 antigen/adjuvant combinations will be assessed simultaneously for a particular endpoint (SCR or SPR) and age category using Bonferroni Type 1 error adjustment. The order of statistical testing is SCR for 18-64 years of age, SPR for 18-64 years of age, SCR for ≥ 65 years of age, SPR for ≥ 65 years of age. Testing will progress in the sequence only if current test is a success, so that no further adjustment of alpha is needed. Success is reached if at least one antigen/adjuvant combination does fulfill the CBER requirements for SCR and for SPR for at least one age category after all permitted statistical tests are completed.

F1: 1.9 µg HA + AS03B; F2: 1.9 µg HA + AS03A; F3: 3.75 µg HA + AS03B; F4: 3.75 µg HA + AS03A; F5: 7.5 µg HA + AS03B; F6: 7.5 µg HA + AS03A

A total of 840 participants are planned to be enrolled, with 60 participants per antigen/adjvant/age group. A drop-out/protocol violation rate of not more than 5% yields an approximate sample size of 57 evaluable participants per group, giving 82% overall power to fulfil the CBER (SCR, SPR) immunogenicity criteria in any one of the 12 adjuvanted vaccine intervention groups, assuming that the reference rate for SPR and SCR is 91% and 80% for participants 18 to 64 years of age and 86% and 75% for participants ≥ 65 years of age, respectively.

The 2-sided exact Clopper-Pearson 99.17% CI for SCR or SPR is to allow parallel assessment of the 6 antigen/adjvant combinations addressing multiple comparisons using a Bonferroni adjustment by dividing the 5% Type I error (two-sided tests) equally 6 ways. Success can be declared for any antigen/adjvant group if CBER criteria is met even if any other group does not meet the CBER criteria.

Table 7 presents the power for 1 group to meet the CBER immunogenicity criteria, assuming the enrollment is 60 participants per group and non-evaluable rate is about 5%.

Table 7 Criteria to Evaluate Primary Objective with Respect to SCR and SPR for Anti-HA, 21 Days After the Second Vaccination

To meet CBER Criteria	Endpoint	Stage in testing sequence	Statistical Success Criteria	N evaluable	Reference value	Power*
18-64 years of age	Anti-HA: SCR	1	LL of 99.17% two-sided CI of SCR > 40%	57	80%	99.99%*
	Anti-HA: SPR	2	LL of 99.17% two-sided CI of SPR > 70%	57	91%	86.26%*
≥ 65 years of age	Anti-HA: SCR	3	LL of 99.17% two-sided CI of SCR > 30%	57	75%	>99.99%*
	Anti-HA: SPR	4	LL of 99.17% two-sided CI of SPR > 60%	57	86%	95.12%*
				Overall power		82%

* Power estimated using PASS 2012, 1-Sided Exact test on the proportions, alpha = 0.415%. Overall power is the product of power for the 4 hypotheses within a formulation across the 2 age groups.

CBER: Center for Biologics Evaluation and Research; CI: confidence interval; HA: hemagglutinin; LL: lower limit; SCR: seroconversion rate; SPR: seroprotection rate.

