8.9. Health outcomes

Not applicable

9. STATISTICAL CONSIDERATIONS**9.1. Statistical hypotheses**

The hypothesis test is planned to demonstrate whether vaccination with monovalent influenza A/Hong Kong/125/2017-like (H7N9) virus vaccine containing 1.9 μg , 3.75 μg or 7.5 μg of HA adjuvanted with AS03A or AS03B elicits an HI antibody response to the vaccine-homologous virus that meets or exceeds the CBER immunogenicity criteria 21 days after the second dose of H7N9 vaccine [[CBER](#), 2007].

Each null hypothesis (H_0) is that the lower limit (LL) of the confidence interval (CI) for seroconversion (SCR)/seroprotection (SPR) rate will not meet or exceed the threshold set in the CBER guidelines. Each alternative hypothesis (H_a) is that the LL of the CI for the SCR/SPR meets or exceeds the threshold set in the CBER guidelines. The overall type I error rate is fixed at 5% for each age group, and a Bonferroni adjustment was applied to allow simultaneous multiple comparisons of each antigen/adjuvant group.

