9.2.1. Immunogenicity

The primary immunogenicity objective of the study is to evaluate whether vaccination with monovalent influenza A/Hong Kong/125/2017-like (H7N9) virus vaccine containing 1.9 μ g, 3.75 μ g or 7.5 μ g of HA adjuvanted with AS03A or AS03B elicits an HI antibody response to the vaccine-homologous virus that meets or exceeds the US Food and Drug Administration, CBER immunogenicity criteria at the Day 43 visit. [CBER, 2007].*

* The age appropriate CBER criteria will be used and assessed separately:

- CBER immunogenicity criteria for SCR for 18 to 64 years of age will be shown if the LL of the 99.17% CI for SCR meets or exceeds 40%.
- CBER immunogenicity criteria for SPR for 18 to 64 years of age will be shown if the LL of the 99.17% CI for the incidence rate of HI Reciprocal Titers ≥ 40 meets or exceeds 70%.
- CBER immunogenicity criteria for SCR for ≥ 65 years of age will be shown if the LL of the 99.17% CI for SCR meets or exceeds 30%.
- CBER immunogenicity criteria for SPR for ≥ 65 years of age will be shown if the LL of the 99.17% CI for the incidence rate of HI Reciprocal Titers ≥ 40 meets or exceeds 60%.

A total of 840 participants are planned to be enrolled, with 60 participants per antigen/adjuvant/age group. A drop-out/protocol violation rate of not more than 5% yields an approximate sample size of 57 evaluable participants per group, giving 82% overall power to fulfil the CBER (SCR, SPR) immunogenicity criteria in any one of the 12 adjuvanted vaccine treatment groups, assuming that the reference rate for SPR and SCR is 91% and 80% for participants 18 to 64 years of age and 86% and 75% for participants ≥ 65 years of age, respectively.

The 2-sided exact Clopper-Pearson 99.17% CI for SCR or SPR is to allow parallel assessment of the 6 antigen/adjuvant combinations within each age group, addressing multiple comparisons using a Bonferroni adjustment by dividing the 5% Type I error equally 6 ways. Success can be declared for any antigen/adjuvant group within an age range if CBER criteria is met even if any other group does not meet the CBER criteria.

Table 14 presents the power for 1 group to meet the CBER immunogenicity criteria, assuming the enrollment is 60 participants per group and non-evaluable rate is about 5%.

Table 14 Criteria to evaluate primary objective with respect to SCR and SPR for anti-HA, 21 days after the second vaccination

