9.5.2. Statistical consideration for interim analysis

Since the primary ***immunogenicity*** endpoints for the study will be complete by the Day 43 visit (collection past Day 43 includes only assessments for unsolicited AEs ***leading to study withdrawal, SAEs, and pIMDs***), no statistical consideration for multiplicity will be given to account for changes in the results reported at the interim analysis compared to the final analysis. **(Amended 22 February 2022)** For the primary immunogenicity analysis, which will be reported at Day 43 the overall type I error rate is fixed at 5% and

a Bonferroni adjustment will be applied to allow simultaneous multiple comparisons of each antigen/adjuvant group. For the primary safety analyses no adjustment for multiple comparisons will be made in each antigen/adjuvant group.

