If statistical analysis cannot be performed for a particular age group or study group, then these should be displayed as “NC.” (not calculated). Confidence intervals that cannot be calculated should be displayed as “(NC.)”.

For the primary immunogenicity analysis, which will be reported at Day 43 the overall type I error rate is fixed at 5% (two-sided tests) and a Bonferroni adjustment will be applied to allow simultaneous multiple comparisons of each antigen/adjuvant group. No further adjustment will be used since the tests will be applied sequentially. For the secondary immunogenicity and primary safety analyses no adjustment for multiple comparisons will be made in each antigen/adjuvant group as the analyses are descriptive. Confidence intervals (CIs) will be presented and p-values will not be presented. For the secondary immunogenicity and safety analyses, CIs are presented for descriptive purposes only.

Baseline will be defined as the value recorded at Visit 1. The study day will be calculated as assessment date - first dose date of study vaccine + 1 if the study date is on or after first dose date of study vaccine, or assessment date – first dose date of study vaccine if the study date is prior to the first dose date of study vaccine.

Throughout the study, logarithmic transformations and anti-logarithms will use base 10.

Statistical analysis will be performed using SAS® Version 9.4 or higher. Standardized and validated SAS macros from PPD will be used to set up table, listing, figure formats (headers/footers and tabulation format) and tabulate the summaries. All tables and listings will be independently validated using double programming; datasets behind the figures will be independently validated using double programming and figure outputs will be independently validated manually.

[figure not shown]

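### The protocol controls type I error separately in each age group, but the SAP tests ≥65 years only after 18-64 years under one overall 5%, without declaring the change; both documents also mislabel the 82% power

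*SAP*

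**What the plan says.** **Protocol.** Section 9.1 states: "The overall type I error rate is fixed at 5% for each age group". Section 9.2.1 applies the six-way Bonferroni correction within each age group and adds: "Success can be declared for any antigen/adjuvant group within an age range if CBER criteria is met". No protocol section orders the two ages. Section 9.5.2 is looser: it fixes an overall rate of 5% without repeating the age split.

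**SAP.** Section 4.2 has one family ("the overall type I error rate is fixed at 5% (two-sided tests") and gives the reason for stopping there: "No further adjustment will be used since the tests will be applied sequentially". Section 4.3 and Table 7 set the order as SCR 18-64, SPR 18-64, SCR ≥65, SPR ≥65, with the rule "Testing will progress in the sequence only if current test is a success, so that no further adjustment of alpha is needed". Where section 4.3 repeats the protocol's Bonferroni and success sentences, the age qualifiers are gone. Section 10.4 repeats the overall 5% and describes the sequence as running for each antigen/adjuvant group. Section 11, which records changes to the protocol's planned analysis, contains only the duration of solicited events.

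**Power.** Protocol 9.2.1 and SAP 4.3 both attach the 82% to any one of the twelve adjuvanted groups. The SAP Table 7 footnote instead defines it as the product over four hypotheses within one formulation and across both ages. Protocol Table 14 has no such note.

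**The concern.** Suppose a formulation misses SPR in 18-64 but meets both criteria in ≥65. Under protocol 9.2.1 that is a formal ≥65 success. Under the SAP the ≥65 tests are not permitted. Both rules are pre-specified, and nothing in the documents says which prevails. Choosing once the Day 43 results are known would be post hoc.

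The gate also sits badly with the SAP's own study-level rule, which needs one formulation to succeed in at least one age category. If the gate is per formulation, ≥65 can never be the only successful age, so the rule reduces to success in 18-64.

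The level of the gate is less clear than it should be. SAP 10.4 and the Table 7 footnote point to a gate within each formulation. SAP 4.3 also says "The 6 antigen/adjuvant combinations will be assessed simultaneously for a particular endpoint (SCR or SPR) and age category", which could be read as letting any passing formulation open the next stage for all six. The figure announced there is not in the copy reviewed and may settle this, so its absence is not counted as a gap.

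**Working it through.** **Inputs** (Protocol 9.2.1 and Table 14; SAP 4.3 and Table 7): N = 57 per formulation and age group; one-sided α = 0.415% (99.17% two-sided interval); SCR/SPR thresholds 40%/70% in 18-64 and 30%/60% in ≥65; reference rates 80%/91% and 75%/86%.

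**Step 1: reproduce the plan's figures.** The cut-off is the smallest x whose Clopper-Pearson lower limit reaches the threshold. Power is P(Bin(57, p) ≥ x).

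| Test | Cut-off | Power |
|---|---|---|
| SCR 18-64 | 34/57 | 0.99988 |
| SPR 18-64 | 50/57 | 0.86259 |
| SCR ≥65 | 28/57 | 0.99999 |
| SPR ≥65 | 45/57 | 0.95120 |

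All four agree with the tables. Let A be the chance that a formulation meets both criteria in 18-64, and B the same for ≥65. As in the plan, the tests are multiplied as if independent; with SCR power near 1 this hardly matters.

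- A = 0.99988 × 0.86259 = 0.8625
- B = 0.99999 × 0.95120 = 0.9512
- A × B = 0.8204, which is the plan's 82%

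**Step 2: what 82% describes.** A given 18-64 group has 86.2%, and a given ≥65 group 95.1%. At least one of twelve is 1 − ((1−A)(1−B))^6 > 99.99%. All twelve is (A×B)^6 = 30.5%. Only one formulation passing in both ages gives 82%.

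**Step 3: power for a formal ≥65 success, one formulation.**

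| Rule | Formula | Reference rates | All rates 3 points lower (assumption) |
|---|---|---|---|
| Protocol, no gate | B | 95.1% | 84.0% |
| SAP, gate per formulation | A × B | 82.0% | 52.4% |
| SAP, gate opened by any formulation | (1−(1−A)^6) × B | 95.1% | 83.7% |

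For the lower rates A = 0.6237 and B = 0.8397.

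**Step 4: chance that the two rules disagree** (≥65 criteria met, ≥65 test not permitted).

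- Per-formulation gate, one formulation: (1−A) × B = 0.1375 × 0.9512 = 13.1%; 31.6% at the lower rates.
- At least one of six equal, independent formulations: 1 − (1−0.1308)^6 = 56.9%; 89.8% at the lower rates. At the reference rates it runs from 36% to 77% over N = 45 to 60.
- Any-formulation gate, six formulations: (1−A)^6 × (1−(1−B)^6), under 0.001%; 0.28% at the lower rates.

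**Step 5: study-level success (SAP rule).** With the gate, 1−(1−A)^6 > 99.99%; 99.7% at the lower rates. Without it, above 99.99% in both cases.

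**Step 6: nominal bound on any false age-group claim** (0.83% two-sided, 0.415% one-sided per claim).

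| Structure | Claims | Two-sided | One-sided |
|---|---|---|---|
| Per-formulation gate | 6 | 4.98% | 2.49% |
| Any-formulation gate | 11 | 9.13% | 4.57% |
| Two age families, no gate | 12 | 9.96% | 4.98% |

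The 11 arises when one truly adequate formulation opens the gate, leaving five 18-64 and six ≥65 groups open to a false claim.

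**The case against.** The strongest reply is that little depends on this. The SAP rule is stricter than protocol 9.1, so no claim becomes less reliable. SAP 8.1 reports the 99.17% intervals by age group whatever the gate allows, and study-level success is near certain. The split also begins inside the protocol, because 9.5.2 already states an overall 5%. All of this is correct, and it limits the effect to a formal ≥65 label. But 9.5.2 sets no test order, while 9.1 and 9.2.1 are explicit about age. SAP 8.1 also says these intervals serve the hypothesis tests, so which tests are permitted matters.

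The any-formulation reading can be called speculative, since SAP 10.4 points the other way. That is fair; the per-formulation reading is the better supported, and the main result uses it. The bounds in Step 6 are nominal. Because the exact test is conservative, attained one-sided SPR errors at N = 57 are 1.17% (per formulation), 1.90% (any formulation) and 2.05% (no gate), all below 2.5%.

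The 56.9% assumes six formulations with identical true rates, which is unlikely across a four-fold antigen range and two adjuvant doses. The 13.1% for a single formulation needs no such assumption.

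Finally, the 82% label is editorial: the arithmetic is right and the SAP footnote defines it correctly. That stands, and it is a minor point.

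**Conclusion.** The concern holds and should be fixed. The protocol and SAP define different error families and different permissions for the ≥65 tests, and SAP 11 does not declare the change. Under the better-supported per-formulation gate, a given formulation's power for a formal ≥65 success falls from 95.1% to 82.0%, about 13 points, at the reference rates with 57 evaluable. The loss grows if the 18-64 rates fall short: with an assumed true SPR of 85% in 18-64, the gated ≥65 power is about 35% against 95% ungated.

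Error is not inflated under that gate. If any passing formulation could open the next stage, the power loss would be negligible, but the nominal bound would exceed 5% two-sided, so the SAP's reason for making no further adjustment would not hold on nominal levels. The 82% is computed correctly and labelled wrongly. Each correctly labelled power is at least 82%, so the sample size is not at risk.

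**What to change.** Before the Day 43 analysis, state one alpha structure identically in Protocol 9.1, 9.2.1 and 9.5.2 and in SAP 4.2, 4.3, Table 7 and 10.4. Either:

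- **(a) Two age families.** Remove the age gate and require SCR and SPR together within an age group. Protocol 9.5.2 must then say that the 5% applies to each age group. The cost is the SAP's single overall 5%: the nominal bound over both ages becomes 9.96% two-sided (4.98% one-sided).
- **(b) Keep the sequence.** Amend Protocol 9.1 and 9.2.1, list the change in SAP 11, and make the SAP 4.3 text state that the gate is per formulation if the figure does not. The cost is about 13 points of ≥65 power for a given formulation at the reference rates.

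Replace the 82% sentence in both documents. Under (a): 86% for a given formulation in 18-64 years, 95% in ≥65 years, and 82% in both age groups. Under (b): 86% for a given formulation in 18-64 years, and 82% for the same formulation in both age groups, which is also its power for a formal ≥65 success. Add the SAP Table 7 footnote to Protocol Table 14.

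Both options change protocol text. Neither changes the sample size, the data collected or the confidence intervals.

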4.4 Randomization, Stratification, and Blinding

The enrollment will be performed to evenly distribute participants across the 2 age groups (18-64 years, ≥ 65 years) (i.e. of the 120 participants in each study group, 60 participants will be aged 18 to 64 years and 60 participants will be aged ≥ 65 years). Within the 18-64 years age group, the enrollment is further stratified into 18-49 years and 50-64 years to allow an even distribution of participants in terms of intervention allocation.

Allocation of the participant to a study group at the investigator site will be performed using central randomization on the PPD Interactive Response Technology (IRT).

The study will enroll approximately 840 participants randomly assigned to 1 of 7 groups of equal size to receive 2 doses of study vaccine or placebo administered intramuscularly 21 days apart. Each participant will participate for approximately 12 months after receipt of the final dose administered.

This is an observer-blinded study. Data will be collected in an observer-blind manner. To do so, vaccine/product will be prepared and administered by qualified study personnel who will not participate in data collection, evaluation, review or the entry of any study endpoint (i.e. reactogenicity, safety, immunogenicity).

The laboratory in charge of the sample testing will be blinded to the intervention assignment. Codes will be used to link the participant and study (without any link to the intervention attributed to the participant) to each sample.

Investigators will remain blinded to each participant's assigned study intervention throughout the course of the study. In order to maintain this blind, an otherwise uninvolved third party will be responsible for the reconstitution and dispensation of all study intervention and will endeavor to ensure that there are no differences in time taken to dispense following randomization.

This third party will instruct the participant to avoid discussing the dosing site or visual appearance of the study intervention with the investigator. Unblinded monitors, and in the event of a Quality Assurance audit, the auditor(s) will be allowed access to unblinded study intervention records at the site(s) to verify that the randomization/dispensing has been done accurately.

The IRT will be programmed with blind-breaking instructions. In case of an emergency, the investigator has the sole responsibility for determining if unblinding of a participants' intervention assignment is warranted.

A statistical team will be unblinded for the interim analysis outlined in Section 10.2 and will prepare the iSRC analyses outlined in Section 10.1.

4.5 Data Handling

Analysis Visit Names for Immunogenicity Analysis

Study visits will be derived as in Table 8. Analysis Visit names (AVISIT) will be used within the Immunogenicity and Safety Analyses.

Table 8 Analysis Visit Names

Visit Name	AVISIT
Visit 1 Day 1	V1 DAY 1
Telephone Contact 1 Day 8	SC1 DAY 8
Visit 2 Day 22	V2 DAY 22
Telephone Contact 2 Day 29	SC2 DAY 29
Visit 3 Day 43	V3 DAY 43
Telephone Contact 3 Month 4	SC3 MONTH 4
Telephone Contact 4 Month 7	SC4 MONTH 7
Telephone Contact 5 Month 10	SC5 MONTH 10
Telephone Contact 6 Month 13	SC6 MONTH 13

Note: Vx = Visit x, SCx=Safety Call x.

Titer Results

For a given participant and a given immunogenicity measurement, missing or non-evaluable measurements will not be replaced. Summaries and analyses will be performed using all available non-missing titer results for the included population.

Titer results recorded as below the cut-off will be imputed with a numeric value of half the cut-off for summaries and analyses and will be listed as reported in the raw data. For example, if an assay records a cut-off of 10 for HI and a sample is reported to have “< 10” as the titer level, a value of 5 will be used for the statistical summaries and analyses. Titer results recorded as “1:x” (where x is the dilution factor) will be assigned a numeric value of x. Titer results recorded as “>1:x” will be assigned a numeric value of x to be used for the statistical summaries and analyses.

The cut-off values for antibody titer are defined by the laboratory before the analysis, and will be specified in the CSR.

Missing Data

For safety analyses, participants who missed reporting symptoms (solicited or unsolicited), concomitant medications, or concomitant vaccinations will not be imputed but will be presented as missing for the summaries.

In order to minimize the effect of missing data, the study period will be divided into time intervals for the safety analyses. For unsolicited AEs, the study period will be divided into the following intervals: all unsolicited AEs and MAEs reported from Day 1 to Day 21 after each vaccination, AEs leading to premature withdrawal from the study during the entire study period, SAEs reported during the entire study period and pIMD reported during the study period for the Exposed Set. Unsolicited AEs will be assigned to the study periods based upon the start date and times recorded in the eCRF. Concomitant medications will be assessed up to 21 days after each vaccination for the Exposed Set in a summary table. All concomitant medications collected in the database will be presented in a data listing.

A participant will be classified as having missing data within the specified intervals as described below:

Category	Regarded as Missing When:
Non serious AEs	No AEs are recorded and there is no response to “Have any non-serious adverse events occurred which are required to be reported as per protocol?” (Non Serious Adverse Event YN electronic Case Report Form [eCRF] page).
Medically attended AEs	If AEs are recorded and there is no response to “Medically attended visit” (Non Serious Adverse Events eCRF page or Serious/Expedited Event eCRF page).
AEs leading to withdrawal from the study vaccine	If AEs are recorded and there is no response to “Action Taken with study vaccine(s) as a Result of the AE” (Non Serious Adverse Events eCRF page or Serious/Expedited Event eCRF page).

Serious AEs	If no SAEs are recorded and there is no response to “Did the subject experience any Serious Adverse Event and/or pIMD and/or other AESI and/or Non-Serious related AE (ADR) that are required to be reported per protocol?” (Serious/Expedited Event YN eCRF page), or if the answer was “Yes” and there is no response to “Serious?” (Serious/Expedited Event eCRF page).
pIMD	No pIMD events recorded and there is no response to “Did the subject experience any Serious Adverse Event and/or pIMD and/or other AESI and/or Non-Serious related AE (ADR) that are required to be reported per protocol?” (Serious/Expedited Event YN eCRF page), or if the answer was “Yes” and there is no response to “Adverse Event of Special Interest (AESI)?” (Serious/Expedited Event eCRF page).
Concomitant medications	If no concomitant medications are recorded on the Concomitant Medications eCRF page, and there is no response to “Have any medications that are required to be reported per protocol been taken?” on the Concomitant Medications and Vaccinations YN eCRF page.
Concomitant vaccinations	If no concomitant vaccinations are recorded on the Concomitant Medications and Vaccinations eCRF page, and there is no response to “Have any vaccines required to be reported as per protocol other than study vaccine(s) been administered?” on the Concomitant Medications and Vaccinations YN eCRF page.

Missing Values for Solicited Adverse Events When Leading Questions Have Been Answered

The eCRF pages Solicited Administration Site Events and Solicited Systemic Events contain the following leading questions:

- Did the subject experience any of the solicited systemic signs/symptoms between Day 1 and Day 7?
- Did the subject experience any solicited administration site events between Day 1 and Day 7?

If the answer is ‘No’ then the investigator is asked not to complete the intensities or measurements for the individual symptoms and individual timepoints. Values in the solicited adverse events dataset will be set as ‘None’ (for intensity) or ‘0’ (for measurement).

The analysis of solicited systemic symptoms will include all subjects for whom the question about the presence of a solicited systemic symptoms has been answered by ‘Yes’ or ‘No’. If the answer is ‘No’, the subject will be considered as not having that symptom after that dose. If the answer is “Yes”, the maximum intensity recording over the considered follow-up period will be used for the analysis of the percentage of subjects with symptoms.

Subjects who documented the presence of a specific symptom (e.g. fever, fatigue, etc.) but partially recorded daily measurement (e.g. intensity missing for Day 3) over the considered solicited period will be included in the summaries and classified according to their maximum observed daily recording over the solicited period.

When no daily measurement is recorded when the presence of a symptom is Yes,

- For the symptoms Headache, Fatigue, Muscle aches, Gastrointestinal Symptoms (nausea, vomiting, diarrhea and/or abdominal pain), Joint Pain, Shivering (chills), and Sweating; those subjects will not be counted in the summary of subjects with a symptoms by grade but will be part of the summary corresponding to the 'All' category
- For Fever, those subjects will not be counted in the summary of subjects with symptoms above a specified threshold, however they will be part of the summary corresponding to the 'All' category.

The analysis of solicited local symptoms will include all subjects for whom the question about the presence of a solicited local symptoms has been answered by 'Yes' or 'No'.

For each solicited administration site symptom, if the answer to the presence of a local symptom is 'No', the subject will be considered not having that administration site symptom at the injection site after that dose. If the answer to is 'Yes', the maximum intensity recording over the considered follow-up period will be used for the analysis of the percentage of subjects with symptoms.

Subjects who documented the presence of a symptom but partially recorded daily measurement over the solicited period will be included in the summaries and classified according to their maximum observed daily recording over the solicited period.

Subjects who have documented the presence of a symptom without any recorded daily measurement from Day 1 to Day 7 will not be counted in the summary of subjects with each grade, however they will be part of the summary corresponding to the 'Any' category.

